In accordance with FERPA, written consent must be obtained to access student records. The consent must: 
 • Specify the records that may be disclosed • State the purpose of the disclosure • Identify the person or class of parties to whom the disclosure can be made 	
 YES (REQUIRED)	I confirm that I will comply with the FERPA policy that is in place at the educational institution where I am conducting my research. This includes, if applicable, the requirements for written agreement when requesting a waiver of consent for personally identifiable information. If an agreement is required, this agreement must be submitted to the IRB.

SECTION V: PROTECTION OF PUPIL RIGHTS AMENDMENT (PPRA):

PPRA is a federal law that affords certain rights to parents of minor students with regard to surveys that ask questions of a personal nature. Research funded by the Department of Education or research conducted in educational institutions that receive funds (for research or other purposes) from the Department of Education must comply with the PPRA.

YES*	NO	
		Does PPRA apply to this study? If YES, refer to the following websites for guidance: 
 • http://www2.ed.gov/policy/gen/guid/fpco/ppra/index.html • http://www.bu.edu/researchsupport/compliance/human-subjects/ If PPRA applies, you must complete the box below:
In accordance with PPRA, written parental consent must be obtained prior to subject's participation in the study.		
 YES (REQUIRED)		I confirm that I will comply with the PPRA policy that is in place at the educational institution where I am conducting my research.

SECTION W: CLINICAL TRIALS REGISTRATION:

The Food Drug and Administration Amendments Act (known as FDAAA 801) requires that “applicable clinical trials” be registered and have results reported on clinicaltrials.gov. In addition, the International Committee of Medical Journal Editors (ICJME) and the National Institutes of Health (NIH) also have requirements for registration. Please see box below to determine if your study requires registration in accordance with either FDAAA 801, ICJME, or NIH.

[figure not shown]
YES	NO	FDAAA 801 Requirements
		Does your study meet the definition of an applicable clinical trial (ACT) and require registration AND results submission in accordance with FDAAA 801? ACTs include: 
 • Trials of drugs and biologics: Controlled clinical investigations, other than phase 1 clinical investigations, of drugs or biological products subject to Food and Drug Administration (FDA) regulation • Trials of devices (see note): 1) Controlled trials with health outcomes of devices subject to FDA regulation, other than small feasibility studies, and 2) pediatric post-market surveillance required by FDA

		Note: If your study meets the requirement for registration and reporting, you must submit the National Clinical Trial (NCT) Identifier # to the IRB prior to IRB approval. NCT #:
YES	NO	ICMJE Requirements
		
Does your study meet the definition of a clinical trial and require registration in accordance with ICMJE?
 
Note: If your study meets the requirement for registration, you must submit the National Clinical Trial (NCT) Identifier # to the IRB prior to IRB approval. NCT #:

YES	NO	NIH Requirements
		
Does your study meet the definition of an applicable clinical trial and require registration AND results submission in accordance with NIH?
 
For more information on this policy please refer to:
 
 • NIH Policy on the Dissemination of NIH-Funded Clinical Trial Information • Checklist 
Note: If your study meets the requirement for registration and reporting, you must submit the National Clinical Trial (NCT) Identifier # to the IRB prior to IRB approval. NCT #:

Certification / Signatures

- By submitting this protocol I attest to the fact that all research activities to be implemented related to human subjects have been completely and accurately described herein.
- I agree to conduct the describe research in an ethical manner.
- I agree to comply with all institutional policies and procedures related to human subjects research and will not begin any human subjects research activities until I have obtained full approval from the IRB.

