Proof-of-concept testing phase (Phase 2): Transition-aged youth on the autism spectrum (ages 14-21) may participate in 2 telehealth sessions and provide written feedback about the program (via post-session feedback forms) if it is appropriate. The participating parents/caregivers will inform the researchers of whether they think their child is able and willing to participate both in the session and/or in completing the feedback form. If necessary, these feedback forms can be completed with the support of a research team member, family member, service provider, or other support person. Youth who participate in the program sessions will be considered research participants, regardless of whether or not they complete the session feedback forms. We will attempt to collect session feedback forms from all autistic youth participants and will track data collection completion as a measure of feasibility. Data will be collected in English.

For both phases of this research, we have chosen to include cognitively-impaired individuals to increase participation of youth across the autism spectrum, including those with accompanying intellectual disability. This decision is consistent with person-centered approaches in autism and disability-related service provision whereby the affected individual

is included in all discussions and decisions about his/her/their care. This inclusive approach is expected to improve the program that is being developed.

In Phase 1, we will enroll linguistically-diverse individuals. Our research group has experience conducting multi-lingual studies, and the PI will closely oversee the work of bilingual research team members who will interact with families in Spanish, Cantonese, Mandarin, and English.

Eligibility Criteria

Members of the research team will conduct a phone screen to ensure eligibility.

Inclusion Criteria:

Phase 1

1. Parents or primary caregivers of transition-aged youth on the autism spectrum:
 - a. Have one or more child(ren) on the autism spectrum who is/are ages 14-21 years old
 - b. Identify as the parent, legal guardian, and/or primary caregiver of the youth
 - c. Speak English, Spanish, Cantonese, or Mandarin fluently
2. Youth on the autism spectrum:
 - a. Have an autism diagnosis OR identify as autistic
 - b. Age 14-21
 - c. Have ability to communicate verbally or in written format
 - d. Speak English, Spanish, Cantonese, or Mandarin fluently
3. Service providers:

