Provide a summary of the consent process, including who will consent participants, when and where consent will occur. The summary should include, as appropriate, any waiting period between informing the prospective participant about the research and obtaining consent, such that the prospective participant or the legally authorized representative has sufficient opportunity to consider whether to participate, and steps taken to minimize coercion or undue influence.

Submit copies of all consent forms and scripts; materials should be submitted as separate documents in Word format.

Adult individuals (parents/primary caregivers, service providers, or young adults on the autism spectrum who are their own guardians) who are interested in hearing more about the study will contact the researchers to express their interest, complete a consent-to-contact form on our study website, or provide verbal consent to professionals or community partners that the research team can reach out to them to provide information about the study.

All informed consent procedures will be carried out by members of the research team who are based at BU or Lehigh University; the Arc partners and Community Advisory Board members will not be involved in obtaining informed consent.

Phase 1 interviews:

Verbal consent will be obtained from parents/primary caregivers, service providers, and 18- to 21-year-old individuals on the autism spectrum who are their own legal guardian. If the individual on the autism spectrum has a legal guardian (ages 18-21) or is under 18 years old, verbal consent will be obtained from the guardian. The research team will learn of guardianship status of the individual on the autism spectrum during the phone screen. A research team member will describe the goals of the study, answer questions, and obtain verbal consent or assent from the participants. Potential participants will have the option of thinking about whether they want to participate. Participants will be provided with a copy of the consent or assent document, and the original will be kept in the confidential research file.

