We also will request, but not require, **individuals on the autism spectrum** to provide consent or assent for their family's participation in the proof-of-concept trial. There are many situations that may preclude obtaining consent/assent from the individual on the autism spectrum or legal guardian; therefore, we will reach out to these individuals to request their consent/assent, but if we are not able to obtain it, we will still enroll the parent / primary caregiver (but the individual on the autism spectrum will only be enrolled if they provide consent/assent). Individuals on the autism spectrum who participate in any program sessions and/or provide session feedback will be asked to provide consent or assent in order to participate.

We will determine whether the individual on the autism spectrum can provide consent or whether he/she/they have a guardian by asking parents and/or service providers during the study screening procedures. Because youth on the autism spectrum will not be completing measures via Qualtrics, we will request verbal consent/assent for their participation in the study. If verbal/nonverbal behaviors indicate the individual on the autism spectrum is unable to provide consent/assent, we will verbally share study information, and ask for verbal assent, with a yes/no response documented by research staff. If no verbal response is provided, we will document this as well, and carefully monitor the individual on the autism spectrum's willingness to participate, and we will continue unless nonverbal behaviors show unwillingness to participate. If the individual on the autism spectrum shows signs of being unwilling to participate, we will move forward with research activities with only the parent / primary caregiver.

For individuals who are not their own legal guardians, there may be situations in which the legal authorized representative provides consent for the individual on the autism spectrum to participate in the study, but the individual on the autism spectrum does not wish to participate. If this occurs, we will first reach out to the individual on the autism spectrum to address any specific concerns about the study. If they still do not wish to participate, the individual on the autism spectrum will not be enrolled, and the legal authorized representative will be informed that the individual on the autism will not be enrolled. In these cases, the parent/primary caregiver can still be enrolled in the proof-of-concept trial.

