Describe the consent and/or assent process for enrolling adults with limited decisional capacity to consent to research. Including how decisional capacity will be determined, and who will serve as Legally Authorized Representative.
For the proof-of-concept trial, we will request – but not require – consent from individuals on the autism spectrum or their legal guardian. The research team will learn of guardianship status of the individuals on the autism spectrum by asking parents and/or service providers during the study screening procedures. We will attempt to obtain assent from the individual on the autism spectrum if possible. If verbal/nonverbal behaviors indicate the individual on the autism spectrum is unable to provide assent, we will verbally share study information, and ask for verbal assent, with a yes/no response documented by research staff.

There may be situations in which the legal authorized representative provides consent for the individual on the autism spectrum to participate in the study, but the individual on the autism spectrum does not wish to participate. If this occurs, we will first reach out to the individual on the autism spectrum to address any specific concerns about the study. If they still do not wish to participate, the individual on the autism spectrum will not be enrolled, and the legal authorized representative will be informed that the individual on the autism will not be enrolled.

Assent will be obtained from:

☐ All Subjects

☒ Some Subjects, specify: Individuals on the autism spectrum who show signs of being unable to provide consent will be asked to provide verbal assent. Other individuals on the autism spectrum who are their own guardians will be asked to provide consent.

☐ No Subjects

☒ Consent will be obtained from the subject's Legally Authorized Representative (LAR) (REQUIRED).

Who will serve as LAR: The individual's legal guardian will serve as the LAR.

CONSENT OF NON-ENGLISH SPEAKING SUBJECTS

N/A ☐

Describe the process for obtaining consent from non-English speaking subjects. List the individual who will serve as the interpreter and his/her qualifications.

NOTE: A copy of the translated consent along with the Attestation Form for Translation of Consent must be submitted. The Attestation Form can be located on the [IRB website](#).

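### In Phase 2, Section K contradicts itself on an 18- to 21-year-old with no guardian who appears unable to consent, and followed as written it can enrol that adult without anyone's consent

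*Combined protocol and SAP*

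**What the plan says.** Section I (Participant Population) sets the Phase 2 youth age range: "Transition-aged youth on the autism spectrum (ages 14-21) may participate in 2 telehealth sessions". Legal adults of 18 to 21 are therefore included. For both phases it adds that "we have chosen to include cognitively-impaired individuals to increase participation of youth across the autism spectrum".

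Section K, under Phase 2 proof-of-concept testing, has staff learn from parents or service providers, at screening, whether the youth can consent or has a guardian. If the youth's behaviour suggests that he or she "is unable to provide consent/assent, we will verbally share study information, and ask for verbal assent". A yes or no answer is documented. If there is no verbal response, that is documented too, and participation goes on unless nonverbal behaviour shows unwillingness. The same text says the youth is enrolled only on giving consent or assent.

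The Section K box on adults with limited decisional capacity divides people by apparent ability: "Individuals on the autism spectrum who show signs of being unable to provide consent will be asked to provide verbal assent". It continues: "Other individuals on the autism spectrum who are their own guardians will be asked to provide consent". It then ticks consent from the subject's "Legally Authorized Representative (LAR) (REQUIRED"), and on who that representative is, it says that the individual's "legal guardian will serve as the LAR". Nobody else is named. The opening of the same box says that consent from the individual or guardian will be asked for but not insisted on.

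Box 2 of Section K (waiver or alteration of consent) is marked not applicable. Box 1 waives only the written documentation of consent.

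**The concern.** The plan sets out to include adults with cognitive impairment, some of whom may be unable to consent and yet have no guardian. For them, one part of Section K requires consent from a representative who does not exist, and other parts offer a way in that needs only assent, or no answer at all. Staff on a consent call could follow either part and believe they were following the protocol.

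At stake is participant protection. Under Section I, a youth who joins a program session is a research participant. Under Sections L and M, sessions are recorded. An adult could be in that position without consent from themselves or from anyone entitled to give it, and without a waiver that covers the case.

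**Working it through.** The point involves no arithmetic, and the plan gives no figure to reproduce. The check follows each kind of Phase 2 youth through Section K as written.

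| Phase 2 youth | What the youth is asked for | Who consents on the youth's behalf | Consent from someone? |
|---|---|---|---|
| Under 18 | Verbal assent | Parent, by verbal script (parental permission box) | Yes |
| 18-21 with a guardian | Assent | Guardian, as representative | Yes, if the required box is applied |
| 18-21, own guardian, appears able to consent | Own consent | Not needed | Yes |
| 18-21, own guardian, appears unable to consent | Verbal assent | Only a guardian is named, and there is none | **No** |

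The last row rests on six steps.

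1. **Is the person eligible?** Yes. The age range reaches 21. The exclusion in Section I concerns inability to share a perspective in speech or writing. A person may be able to do that and still be unable to give informed consent, so the exclusion narrows the group without emptying it.
2. **Which branch applies?** The limited-capacity box first sends those who show signs of being unable to consent to verbal assent, with no condition on guardianship. It then asks the *other* own-guardian individuals for consent. That word places an own-guardian adult who seems unable to consent in the assent branch.
3. **Is there a representative?** The guardian is the only one named, and no substitute is offered.
4. **Is the enrolment rule met?** The Phase 2 text accepts consent or assent and does not say when assent is enough by itself. Verbal assent satisfies it on its face.
5. **What if there is no answer?** The Phase 2 text continues unless unwillingness is shown. This does not fit the rule that the youth is enrolled only on giving consent or assent, and it removes even the assent.
6. **Does a waiver cover the case?** No. Box 2 is marked not applicable, and Box 1 concerns paperwork, not consent itself.

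Against steps 2 to 5 stands the ticked requirement for representative consent. If it governs, the person in the last row cannot be enrolled. No sentence in Section K says so, and none says which text prevails.

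**Number affected.** Section I gives 20 families in Phase 2 with at most one autistic individual each, and youth join only when possible. The documents give no age distribution, no share under guardianship and no share unable to consent. The number therefore cannot be derived.

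**The case against.** The strongest reply is the ticked box. Representative consent is required for adults with limited capacity, the guardian is the representative, and so an adult with no guardian cannot be enrolled. On this view the statement that youth consent is requested but not required concerns only the family's participation, because the Phase 2 text uses it to let the parent enrol alone. The phrase combining consent and assent is then shorthand for whichever applies to the person's legal status.

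Much of this is fair. It shows that the plan does not openly permit enrolment without consent. It does not remove the conflict. The limited-capacity box repeats the not-required wording without tying it to the family's participation, routes people to assent without regard to guardianship, and never states that a person without a representative is left out.

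A reader might also infer several stronger points that the documents do not support:

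- **The same gap in Phase 1.** Section I makes ability to consent a condition for Phase 1 youth and reserves assent for those who are not their own guardian. Section K, under Phase 1 interviews, takes consent from "18- to 21-year-old individuals on the autism spectrum who are their own legal guardian". The gap is specific to Phase 2.
- **No check of understanding anywhere.** How capacity is determined is described thinly. However, consent scripts are submitted as separate documents and are not available here, so the absence of such a check cannot be shown.
- **A headcount.** Any figure would need an assumed share with no basis in the documents, and would have to treat 20 families as 20 participating youth.
- **Unusable data.** Nothing in the documents says that recordings or interviews from these youth would have to be discarded.

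**Conclusion.** The point holds for Phase 2 as a contradiction within Section K. For an 18- to 21-year-old without a guardian who appears unable to consent, the required-representative box leads to no enrolment. The assent branch, the consent-or-assent rule and the rule on silence can lead to enrolment with no consent from anyone. The second outcome follows from the stated rules, so it is more than a missing detail.

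The group is probably a small part of at most 20 youth, but its size is unknown, and the conclusion does not depend on it. It rests on a literal reading of Section K and on the possibility that at least one such adult is approached. No view is taken here on the legal force of assent under rules outside the documents. The matter concerns participant protection and should be settled before Phase 2 youth are approached. It does not by itself undermine the trial's feasibility or acceptability analyses.

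**What to change.** Amend the Phase 2 text and the limited-capacity box in Section K so that both say the same three things:

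1. Assent is sufficient only when a guardian, or a parent for a minor, has also consented.
2. A youth aged 18-21 who has no guardian and cannot give consent is not enrolled as a research participant. The family continues through the parent-only route that already exists: parent enrolment alone in Section K, and the alternate Session 3 in Section L.
3. What happens after no verbal response is brought into line with the rule that a youth is enrolled only on giving consent or assent.

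A mandatory teach-back for every own-guardian adult is not needed to resolve the contradiction.

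The cost is a few sentences in two places, plus matching wording in the youth consent and assent script. Section L already foresees an amendment before Phase 2 starts, which could carry the change. The downside is that a few youth would contribute no session feedback or exit interview of their own, in a study that set out to hear from youth across the spectrum. Their families would still receive the program, and their parents would still provide data.

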By signing this form, you are indicating that you have reviewed the application, that you agree to serve as the Co-PI for this study with the student and that you will be responsible for the ethical conduct of this student's human subjects research.

Faculty Advisor (print name):

Signature:

Date:

IRB School Reviewer, if applicable (print name):

Signature:

Date:

Statistical Analysis Plan

To assess clinically-significant change in treatment targets and outcomes, we will use both anchor-based and distribution-based approaches. Regarding anchor-based approaches, we will assess changes on proposed treatment targets (parent self-efficacy and expectations for adult outcomes) and program outcomes (transition planning activities and attainment of personalized program goals) in relation to self-reported global assessment of change. Global assessments are considered to be sensitive to change and are obtained by asking participants to think back over a specific period of time (i.e., since before participation in Families FORWARD) and indicate the presence and direction of change in their functioning from that time to the present (i.e., improvement, decline, no change). We will use Pearson correlations to assess associations between global assessment ratings and pre/post-program change scores on treatment targets and outcomes. Regarding distribution-based approaches, we will compare pre- to post-program changes in treatment targets and program outcomes to measures of variability within the sample. We will complete these analyses using standard errors of measurement (SEM), standard deviations (SD), and effect sizes (ES). SEM of 1.0, SD of 0.50, and/or ES (Cohen's d) of 0.20 will be indicative of clinically-significant change. We will analyze qualitative exit interview data using applied thematic analysis. Although our sample is not large enough to reach saturation within each racial/ ethnic group, a nuanced analysis according to race/ethnicity is important for our research question that addresses feasibility, acceptability, and perceptions of program benefit across diverse participants. The goal of proof-of-concept testing is not to demonstrate thematic saturation, but rather, to inform the promise of an intervention to guide future work. We will conduct all analyses for the entire sample and again separately for each racial/ethnic group (Black, Latinx, Asian, and non-Latinx white), since outcomes may differ across groups.

To assess acceptability, descriptive statistics (mean, median, standard deviation) will be calculated for quantitative acceptability ratings. Exit interview data about program usefulness and value will be evaluated using applied thematic analysis. Analyses will be conducted with the whole sample and separately for each racial/ethnic group. To assess feasibility, we will calculate the number of eligible participants who enrolled in the pilot trial. Retention will be presented descriptively as the average number of sessions completed and follow-up rates within each racial/ethnic group. To assess selective attrition, we will use t-tests and chi squares to evaluate the demographic and autism-related characteristics of families who complete the program vs. those who do not complete the program; these analyses will be conducted for the entire sample. To assess feasibility of the telehealth approach, we will capture technology issues during review of session recordings and will track the number of families who required a tablet to be loaned to them in order to participate in the program.

To assess viability of research procedures and measures, rates of completion for pre- and post-program measures will be described descriptively. We will use t-tests and chi squares to evaluate the demographic and autism characteristics of families who complete the measures vs. those who are lost to follow up; these analyses will be conducted for the entire sample. To assess participant understanding of measures, missing data and inconsistent response patterns will be recorded. Data collection time will be calculated descriptively (mean, standard deviation, range); participant burden regarding completing study measures will be captured qualitatively during exit interviews and will be summarized using applied thematic analysis. Fidelity to the program manual will be assessed by evaluating session recordings against checklists of required components and calculating the percentage of required components present.

